- A. After pre-study consent, the day prior to colonoscopy for colon cancer screening/detection, a stool (patient-collected) sample will be collected prior to bowel prep for colonoscopy. If, for some reason, this is not possible to do by the patient, then the physician will collect a rectal swab during colonoscopy (**Visit 1**). One stool sample (self-collected) the day prior to the first outpatient appointment before start of treatment (between Days 21-28) – Pre-Treatment (**Visit 2**) 3. Once IV chemotherapy begins, this will be designated at treatment day 1 (TD1). After the IV chemo rounds 2 (**Visit 3, treatment day 15**), 6 (**Visit 4, treatment day 71**) and 10 (**Visit 5, treatment day 128**), stool will be collected by the patient at home the day before starting chemo and on the 2nd day (or within 72 hours to account for constipation/diarrhea) after the last treatment day of that round of IV chemo for that session. Specifically, one stool will be collected on TD 15 and 19 (or the day before the next IV chemo round starts) after the 2nd round of IV chemo; on TD, 71 and 75 (or the day before the next IV chemo round starts) after the 6th round of IV chemo; and on TD 128 and 131 (or the day before the next round of IV chemo) after 10th round of IV chemo treatment. Blood draw is SOC, however, stool samples will be requested in addition to SOC.
- B. A blood sample taken at the same time as blood is draw for standard clinical treatment when the patient goes in for the clinical visit or treatment by the REA during usual blood draw times (Surgery Day and on the outpatient visit prior to treatment; Treatment Days 15, 71, 128).
- C. Tissue samples from the patient's resected tumor and non-tumor adjacent tissue after resection surgery will be collected for 1) fresh/frozen and 2) Carnoy's fixitive. Specifically, the physician will take a larger piece of both tumor and non-tumor adjacent tissue so that a small piece of each can be stored for analysis. After specimen collection and ID coding, microbial DNA will be isolated from the microbiome specimens and fecal and circulating metabolites identified. The DNA will be used to conduct microbial DNA sequencing (metagenomics) in accordance with existing protocols through the Integrated Human Microbiome Project (iHMP) study of IBD. The fecal metabolites will be used

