**The first study visit** (2 hours) will occur at the BSWH center at which they were initially given the diagnosis of CRC. This visit will occur after consent (after colonoscopy and stool collection at baseline) and screening has occurred and prior to surgery or anti-cancer treatment is initiated. For stool samples, subjects will be given a bag with collection devices, a **Stool Collection History Form**, and instructions (**Comprehensive Stool Kit FED EX Ready**) for collecting stool and contacting the REA for stool drop off or pick up (**instruction for Retraining Your Specimen Samples**). The patients will also be provided with a mailer box if they would rather mail in their specimen, which is stable on ice packs (provided with stool kit) for 24 hours. Prior to Visit 2, patients will complete 2 online dietary assessment tools, the food frequency questionnaire called the **DHQIII (an online survey that takes 30-60 minutes)** and **24-hour recall called the ASA24 (an online survey that takes 20-30 minutes)**, at home prior to their outpatient visit (after surgery) and prior to the beginning of treatment. If the participant needs assistance with either of these surveys, the REA will guide the patient through the online assessment from their computer. This dietary assessment tool is well validated and has been used in numerous large population studies for collection dietary pattern information. Participants will also complete a medical history questionnaire (**COLON-MD Questionnaire 2020-2023**) in an interview with one of the BSW REAs at the time of their first visit.

On the day of surgery, blood will be collected as part of SOC. During surgery, tissue will also be collected from resection, tumor and non-tumor adjacent (2 of each; one for frozen and one for fixation).

**The second study visit** (1 hour) will take place approximately three to four weeks (weeks 3 or 4) after surgery in the outpatient clinic. During this study visit, an additional 2 vials of blood will be taken at the same time as part of the routine clinical visit, and the patient will be given another stool sample kit to take home to collect stool and instructions. The patient will again be asked to take the 24-hour recall online (**ASA24**) complete it at home online within 72 hours of producing the stool sample, and complete the **Stool Collection Form**.

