and microbial clusters (community state types) at baseline using Kruskall-Wallis, and for individual taxa using Pairwise Spearman correlations. We will use PERMANOVA for comparing beta-diversity (weighted UniFrac distances) at baseline by levels of macro- and micronutrients. DESeq2, Kruskall-Wallis and Mann-Whitney tests will be conducted to identify significant differences in tissue and stool taxa or microbial clusters according HEI scores at baseline. The Benjamini and Hochberg false discovery rate (FDR) will be used to correct for multiple testing. Taxa or microbial clusters found to be significantly differentially abundant between treatment time points and baseline will be used to conduct 'random forest' modeling, as previously described, to identify dietary factors that best predict changes in these taxa or clusters. Additionally, we will investigate the tissue and stool microbiome-diet relationship using principal components analysis to identify significant trends among the dietary factors using coinertia analysis. To investigate the microbiome-diet relations during treatment, we will use the microbial clusters and calculate the  $\log_2$  fold change in the clusters from baseline. We will then determine how much the clusters change from baseline according to dichotomous values of macronutrients.

**Microbiome-treatment analysis:** To evaluate differential abundance comparing treatment time points to baseline (prior to surgery and post-surgery/pre-treatment), DESeq2 will be used to control operational taxonomic unit (OTU) over-dispersion between replicates; OTUs will be considered significantly differentially abundant between time points if the false discovery rate (FDR) corrected p-value is below 0.1. A change in relative abundance will be defined as a fold change between mean log relative abundance during treatment phase (week 4, 14, 24) and baseline (prior to surgery). Taxa found to be significantly differentially abundant between treatment time points and baseline (FDR corrected p-value  $<0.05$ ) will be put into an adjusted regression model to control for age, education, income level, marital status, and activity level, diet quality (HEI), tumor stage, medical history with p-values corrected for multiple hypothesis testing using FDR adjustment.

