**Community state type modeling of treatment effect:** As described earlier, in order to reduce data dimensionality and improve power (due to small sample size), we will perform cluster modeling using Dirichlet multinomial mixtures, as well as, use the partitioning around the medoid (pam in R) algorithm. To calculate the dissimilarity matrix for this analysis, we will first calculate weighted UniFrac distance, then this matrix will be dimensionally reduced by choosing the most significant eigenvectors from PCoA analysis. Community state types (CST), which are defined as 'clusters of community samples with similar compositions of microbial taxa', will be obtained from this analysis. Statistical difference in CST abundance between treatment and baseline will be conducted using median values. Plots of CSTs for each subject over time will be used to identify associations between CSTs and incidence of CID, mucositis and severity of side effects. In order to model the dynamics of the CST transitions, we will use Markov chain to estimate the transition probabilities, as demonstrated for vaginal CST associated with pre-term birth. Transition rates between CSTs for each set of paired samples will be calculated using maximum-likelihood estimates. Additionally, differential relative abundance analysis of CSTs between baseline (pre-surgery and pre-treatment) and treatment time points will be conducted using linear mixed models to account for the repeated measurements at the 4 time points and missing observations. To evaluate differences in beta diversity between treatment and baseline the PERMANOVA test will be used. The inferred function of the microbiota will be obtained using the bioinformatics tool PICRUSt, which uses 16S rRNA marker genes to predict presence of gene families and construct a composite metagenome. This method has been used successfully in several similar studies to predict key metabolic functions associated with taxa important in distinguishing disease from healthy controls.

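### Microbiome change is defined at treatment weeks 4, 14 and 24, which fit the scheduled stools under no time origin, and against a pre-surgery reference that cannot be read as change during FOLFOX

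*Protocol*

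**What the plan says.** All of the following is in the Protocol.

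- **Change definition** (Section 4.4, Microbiome-treatment analysis): "A change in relative abundance will be defined as a fold change between mean log relative abundance during treatment phase (week 4, 14, 24"). The reference is the pre-surgery sample alone: "during treatment phase (week 4, 14, 24) and baseline (prior to surgery"). No origin is given for the weeks.
- **Sentence just before it**: the DESeq2 test is described as "comparing treatment time points to baseline (prior to surgery and post-surgery/pre-treatment"), which is two baselines.
- **Section 4.4, Community state type modeling**: the mixed model also works "between baseline (pre-surgery and pre-treatment) and treatment time points", and is meant "to account for the repeated measurements at the 4 time points and missing observations".
- **Schedule** (Section 4.1, items A and B; Section 4.3, third to fifth visits): Visits 3, 4 and 5 are at rounds 2, 6 and 10, on TD15, TD71 and TD128. Each has one stool before the round and one after it (about TD19, TD75 and TD131, or as late as the day before the next round).
- **Visit 2**: the post-surgery, pre-FOLFOX visit is "approximately three to four weeks (weeks 3 or 4) after surgery in the outpatient clinic".
- **Sub-Aim 1a** (Section 3) asks for three time points during FOLFOX.

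**The concern.** The sentence fixes which samples make up the on-treatment mean and what they are compared with. If its weeks do not correspond to scheduled samples, an analyst has to override the written rule to apply it, and two analysts may do so differently.

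The reference matters separately. Between the pre-surgery stool and Visit 2 the patient has bowel preparation, surgery and pre-operative intravenous antibiotics, which Tissue Biofilm Quantification says are given in all cases. Change from the pre-surgery stool includes whatever of that has not recovered. Reported without a label, it could be taken for a FOLFOX effect.

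Microbiome change is listed as a primary outcome in Section 3 and as a secondary endpoint in Section 4.3, so the measure deserves an unambiguous definition.

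**Working it through.** **1. Scheduled stools in weeks from TD1.** Week = TD/7, rounded up.
- Visit days: 15/7 = 2.14, week 3; 71/7 = 10.14, week 11; 128/7 = 18.29, week 19.
- Post-round stools: 19/7 = 2.71, 75/7 = 10.71, 131/7 = 18.71; again weeks 3, 11 and 19.
- Gaps between visits: 71 − 15 = 56 days; 128 − 71 = 57 days.

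**2. The stated weeks.** Weeks 4, 14 and 24 are 10 × 7 = 70 days apart. As seven-day blocks they are days 22–28, 92–98 and 162–168. Rounds are 14 days apart, from (71 − 15)/4 = 14. With round = whole part of (day − 1)/14, plus 1, these blocks fall in rounds 2, 7 and 12 if counted from TD1. The visits are at rounds 2, 6 and 10.

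**3. Could another origin fit?** Moving the origin shifts all days equally and leaves the spacing unchanged. Two samples can carry two week labels only if the largest possible gap between them reaches the smallest gap between the labels.
- Smallest gap between adjacent labels: 92 − 28 = 64 days. Smallest gap from week 4 to week 24: 162 − 28 = 134 days.
- Stools on scheduled days, including the day-before stool (TD14–19, TD70–75, TD127–131): the largest adjacent gaps are 75 − 14 = 61 and 131 − 70 = 61, both below 64. No two adjacent labels fit. The full span is 131 − 14 = 117, below 134. At most one label can be met.
- Widest windows, up to the day before the next round (TD14–28, TD70–84, TD127–141): 84 − 14 = 70 exceeds 64, so two labels can be met. The full span is 141 − 14 = 127, still below 134, so three cannot. Strict 14-day rounds from TD1 would end the last window at TD140, which only shortens the span.
- A search over origin shifts of −400 to +400 days gives the same result: at most one match on scheduled days and two with the widest windows, never three.

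Counting from surgery, with 21, 28 or 35 days added to the treatment day, puts Visits 3–5 in weeks 6, 14, 22; 7, 15, 23; or 8, 16, 24.

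**4. Distance from the samples on the TD1 clock.** Week 14 starts 92 − 75 = 17 days after the scheduled Visit 4 post-round stool, or 92 − 84 = 8 days after the latest one. Week 24 starts 162 − 131 = 31 days after the Visit 5 post-round stool, or 162 − 141 = 21 days after the latest one.

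**5. Reference.** On the log scale:

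on-treatment − pre-surgery = (Visit 2 − pre-surgery) + (on-treatment − Visit 2)

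The first bracket is the perioperative change and enters in full. The second is the change during FOLFOX. The Protocol gives no figure for the first bracket.

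**6. Number of time points.** Two baselines plus three treatment visits make 2 + 3 = 5. This agrees with the five occasions listed under Data Collection (Stool microbiome) and with 560 stools from 112 people (560/112 = 5, Sample Population). If both stools per treatment visit enter, the count is 2 + 3 × 2 = 8, which agrees with $20 per stool up to $160 (160/20 = 8, Section 4.3). Four results only if the two baselines are pooled (1 + 3), which the text does not say.

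**The case against.** **The visits can be recovered.** There are three treatment-phase labels and three treatment visits, so Visits 3–5 are almost certainly meant. That largely stands and limits the harm. It does not make the written rule correct, nor does it say which of the two stools per visit enters.

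**A stronger reading.** A reader might infer that week 4 means Visit 2, since Section 4.3 places that visit in weeks 3 or 4 after surgery, and that a pre-FOLFOX sample would then dilute the on-treatment mean. The Protocol does not support this. Section 4.1 starts treatment at the first infusion and labels Visit 2 pre-treatment, and the sentence before the definition classes that sample as a baseline. The calendar does not support it on scheduled days either. Counting from surgery, Visit 4 stools at TD70–75 fall in week 14 only if TD1 is on day 18–29 (92 − 74 to 98 − 69). Visit 5 stools at TD127–131 fall in week 24 only if TD1 is on day 32–42 (162 − 130 to 168 − 126). These ranges do not overlap; a fit needs the Visit 5 stool to slip to TD134 or later.

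**The reference may be deliberate.** The Introduction counts surgery as part of standard treatment, and Aim 1 asks about response to cancer treatment. So the pre-surgery contrast is legitimate. A reader might also infer that no comparison with the post-surgery sample is planned; that would be wrong, because the DESeq2 and mixed-model comparisons already name both baselines. What remains is that the test and the change measure rest on different references without explanation, and that the measure is not labelled as including perioperative change.

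**Conclusion.** The concern holds as a wrong and incomplete analysis definition. The labels for weeks 4, 14 and 24 match Visits 3–5 under no time origin: the longest possible sample span is 127 days against a required minimum of 134. This rests on the planned schedule and on the 14-day spacing implied by TD15 to TD71; delays in individual patients could stretch the spacing but would not explain a planned week 24.

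The fold change from the pre-surgery stool is a valid total-treatment contrast but cannot be read as change during FOLFOX. The perioperative share is carried over in full, and its size is unknown from the Protocol. The count of 4 time points conflicts with the 5 (or 8) that the schedule gives.

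The consequence is limited to the microbiome-change results. The models in Section 4.4 that predict or classify CID do not use this definition, and no sample is lost.

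**What to change.** - Replace the week labels with Visits 3–5 (rounds 2, 6 and 10) and their scheduled treatment days. State whether the pre-round stool, the post-round stool or both enter.
- Report the fold change from the post-surgery, pre-FOLFOX stool as change during FOLFOX. Keep the fold change from the pre-surgery stool as a separately labelled total-treatment contrast.
- Enter the two baselines as distinct levels in DESeq2 and in the mixed model.
- Correct the number of time points to 5, or to 8 if both stools per treatment visit are modelled.

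These are text edits; every sample is already scheduled. The cost is at most one extra reported contrast per taxon. Without a concurrent control, the FOLFOX contrast may still overlap with recovery from surgery and antibiotics, and the report should say so.

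A side matter, on which the point does not depend: Section 4.1 has the Visit 2 stool collected "the day prior to the first outpatient appointment before start of treatment (between Days 21-28"), while Section 4.3 says that at that visit "the patient will be given another stool sample kit to take home to collect stool and instructions". As this stool anchors the FOLFOX contrast, the two passages should be reconciled in the same edit.

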The REA will pre-screen patients that are scheduled to undergo colonoscopy to identify patients as a potential study participant. Patients scheduled to undergo colonoscopy for suspected colon cancer will be approached by the REA or Physician to ask if they would like to participate in the study and enrolled if they give consent. These informational sources will provide a short description of the study purpose and requirements for participation. Written informed consent will be obtained by the REA from patients agreeing to participate in the study and before commencement of any study activities. Once identified, the REA will screen the patients and obtain consent for study entry. After consent, participating patients will be provided with a study identification number. This number will be utilized on the data collection form, sample labeling and dietary assessments to promote confidentiality throughout the study procedures. At the consent visit, patients will complete a data collection form utilized to confirm study eligibility and record interval history at the sampling time points. Next, they will be given a stool collection kit to take home along with their bowel prep kit, to collect stool prior to bowel prep. If a positive CRC diagnosis is made through the pathology department and confirmed by GI physicians at BSWH facilities, they would continue as a participant in study. This method will allow the collection of stool specimen prior to colonoscopy. **If they are not diagnosed with stage II/III CRC, subjects will be asked if the stool sample can be used in the study as a control. Subjects will be given the option to agree or decline on the prescreening consent form.** [name] will direct the longitudinal specimen collections, assessments and retention. This consent information will be kept at BSWH by either the REA in a password protected file only accessible by the REA or [name]. We plan to recruit 112 stage II/III patients, (110% of what is needed according to power calculations). Recruitment and sample collection will be supported by the clinical practice sites in Temple and Waco, REAs, and facilitated by Principle Investigator [name] PhD, MPH, RD and Physician Drs. [name].

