##### **Study procedures:**

This study will collect two sets of data from subjects at baseline (pre-treatment) and on-treatment, as outlined in the Study Design section above.

After specimen collection and coding, microbial DNA will be isolated from the microbiome specimens and fecal metabolites identified. The DNA will be used to conduct DNA sequencing (metagenomics) in accordance with existing protocols through the Integrated Human Microbiome Project (iHMP) study of IBD. The fecal metabolites will be used to produce spectral profiles for quantification using protocols from the iHMP. RNA will be isolated from tissue samples and separate section preserved in Carnoy's to determine biofilm formation. RNA will be used to conduct gene expression assays to confirm taxa identified from sequencing, and blood samples will be used to conduct cytokine assay.

In compliance with BSW protocols, subjects will be screened after consent to verify eligibility. No interventions, device or drugs will be used as part of this observational study. Each participant will serve as his or her own control for the observational (and large cohort) study since this is a prospective cohort design, thus no randomization procedures will be employed. In addition, the questions being asked (e.g. whether the stool microbiome is predictive of treatment toxicity) are dependent upon the participant's baseline data.

This study will consist of potentially five study visits as described below.

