
#### *Medical and Symptom History:*

Specific subject information will be collected via review of the medical record(s). Specifically, data will be collected apart from that captured on the medical record, which will include minimal information on socioeconomic status (education, income), tobacco and alcohol history and medication history (**COLON-MD Questionnaire 2020-2023**). At each clinical visit after surgery and during the treatment time points, the REA will assess mucositis and diarrhea grade using the **CTCAE – Gastrointestinal/Diarrhea, Grade 1-5**.

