#### **4.4 Data Analysis.**

Classification of taxa associated with side effects or severity: Recently, in an animal model of colon tumorigenesis (AOM/DSS), investigators used the initial microbial community structure (16s rRNA sequencing) to predict tumor burden after exposure to various antibiotics during colon carcinogenesis. In order to conduct a similar analysis and reduce data dimensionality, we will first perform cluster modeling using Dirichlet multinomial mixtures (Holmes et al. 2012) to identify microbial clusters (community state types). To determine which taxa or taxonomic cluster are the best predictors of treatment side effects (CID, mucositis) and severity (stage 3-4), we will conduct 10-fold cross-validation using the RandomForest package (Version 3.6.4) in R (R-studio, Version 0.98.1091; Boston, MA). Specifically, 5,000 trees will be used and the parameter mtry will be set at 100. The taxa with the highest importance scores will be used for further analysis. This procedure will be tested by splitting the data into test and training sets, then running Random Forest using the same procedure described above on the training dataset and comparing the predictive accuracy of the top taxa (based on importance scores) in the test set. Based on this 10-fold cross-validation, we will be able to calculate sensitivity and specificity. These top taxa will then be used to generate receiver operator curves (ROC) and calculate area under the curve (AUC). Each microbial cluster or taxa will undergo independent logistic regression testing to calculate area under the ROC curve using Stata (v13). The command roccomp will be used to compare statistical difference between AUCs and determine the best combination of taxa for classification of CID or mucositis and for severity.

Microbiome-Diet Analysis: To evaluate the impact of diet on the stool and tissue microbiome, we will use the dietary analysis generated from the ASA24 and DHQIII, which includes the Healthy Eating Index (HEI). Prior to analysis, we will conduct normality testing for each variable using Shapiro-Wilk test. For any variables that do not pass, a logarithm transformation will be performed. In order to identify any potentially important diet or nutrient-microbiome associations, we will conduct correlation analysis between dietary macronutrients (carbohydrates, fats, proteins) or micronutrients (vitamins and minerals)

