**Metabolite-CID analysis:** In a similar manner to the Microbiome-CID analysis, we will conduct logistic regression analysis between CID (present/absent) and metabolites at baseline, and at individual time points controlling for multiple hypothesis testing (FDR  $<0.05$ ). Further, principal component analysis and partial least squares-discriminant analysis will be conducted to determine the metabolic alteration between CID and nonCID subjects after mean centering and unit variance scaling. The variable importance scores of all of the peaks for the tenfold cross-validated PLS-DA model will be considered for

peak selection and biomarker classification. Additionally, metabolites found to be significantly different between treatment time points and baseline will be put into an adjusted linear mixed model regression.

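### The protocol adjusts the within-patient time contrast for mostly fixed patient traits without stating a patient term, and writes the between-patient CID association models without covariates

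*Protocol*

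**What the plan says.** **Time contrast.** In section 4.4, under Microbiome-treatment analysis, DESeq2 compares treatment time points with baseline. Then "Taxa found to be significantly differentially abundant between treatment time points and baseline" go forward and "will be put into an adjusted regression model to control for age, education, income level, marital status, and activity level"; the list continues with HEI, tumor stage and medical history. Section 4.3 (Study procedures) states the design: "Each participant will serve as his or her own control". No patient term is stated for DESeq2 or for the regression. The initial comparisons between time points (Bioinformatics overview) use Mann-Whitney tests, which are unpaired. Linear mixed models for repeated measures are named for community state types, cytokines and the follow-up of metabolites that change over time, but not for this taxon analysis.

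**CID models.** Under Metabolite-CID analysis, "we will conduct logistic regression analysis between CID (present/absent) and metabolites at baseline, and at individual time points controlling for multiple hypothesis testing". No covariates are named. The one adjusted model in that paragraph is again entered through the treatment-versus-baseline contrast. For taxa, "Each microbial cluster or taxa will undergo independent logistic regression testing to calculate area under the ROC curve", also without covariates. Sub-Aim 1b (section 3) asks for associations of pathways and metabolites with CID incidence and severity.

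**Data available.** Medical and Symptom History names "minimal information on socioeconomic status (education, income), tobacco and alcohol history and medication history" as collected beyond the medical record. The consent-visit form is also used to "record interval history at the sampling time points". Marital status and activity level appear only in the covariate list.

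**The concern.** Fixed traits threaten the two kinds of comparison differently. When a patient's treatment stool is compared with that patient's own baseline stool, age, education, income and stage are the same on both sides. When patients with CID are compared with patients without it, those traits can differ and can drive both the marker and the outcome. The protocol itemises its adjustment for the first comparison and writes the second without any.

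Two things are at stake. First, without a patient term the time contrast depends on the measured covariates to absorb differences between patients, and missing visits let those differences into the estimate. Second, a metabolite or taxon can be reported as associated with CID, a primary outcome, because it tracks age, stage or smoking.

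**Working it through.** The protocol gives no figure for this point, so there is none to reproduce. Both checks below are simulations in which the true effect is zero.

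**1. Time contrast (400 runs per setting)**

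Inputs: 112 patients (protocol, section 4.3). Assumed: outcome = 0.8 × covariate (in SD units) + patient effect (SD 0.5) + error (SD 0.5), measured at baseline and once on treatment, with no true change.

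- Complete pairs: the mean time coefficient was 0.0055 with and without the fixed covariate. The largest difference in any run was 1.5e-15. Adjusting for a fixed trait does not move the estimate.
- Missing treatment visits: probability of loss = 1/(1 + exp(1.1 − covariate)), which loses about 29%. The unpaired, unadjusted estimate was −0.19. The covariate-adjusted estimate was 0.002 and the paired estimate −0.0002, both about zero.

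Adjustment worked in the second case because the trait driving dropout was the one measured. With two time points, the paired estimate is the one that a patient fixed effect gives. It needs no list of traits, because every fixed trait drops out of the within-patient difference. It does not cure dropout that depends on the change itself.

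**2. CID models (1,000 runs per setting)**

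Inputs: 112 patients. CID rate 50%, taken from the Significance section, which says CID affects over half of patients. Assumed: a standard normal confounder C; a marker with correlation r to C; logit P(CID) = b × C; no effect of the marker on CID. Two-sided test at 5%.

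| r (marker, confounder) | b per SD (odds ratio) | False positives, unadjusted | False positives, adjusted for C |
|---|---|---|---|
| 0.2 | 0.4 (1.5) | 5.8% | 4.4% |
| 0.3 | 0.7 (2.0) | 18.0% | 4.8% |
| 0.4 | 0.7 (2.0) | 22.9% | 4.7% |

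The Monte Carlo error of a 5% rate is sqrt(0.05 × 0.95 / 1,000) = 0.7 points, so the first row cannot be told apart from 5%. A binary confounder (40% prevalent, odds ratio 2-3 for CID, marker shift 0.4-0.8 SD) gave 7.1% to 16.5% unadjusted, inside the same range.

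**3. Room for adjustment**

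Events: 112 × 0.5 = 56.

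- All eight listed covariates at one parameter each, plus the marker: 56 / 9 = 6.2 events per parameter.
- Five covariates plus the marker: 56 / 6 = 9.3.

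A short set is affordable. Moving the whole list across is less so.

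**The case against.** Several stronger readings are tempting, and the protocol does not support them.

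- *Fixed traits cannot confound the time contrast, so the listed adjustment does nothing.* This holds only for a paired analysis with complete pairs. No pairing is stated, and the protocol expects missing observations, so the listed covariates can remove some bias (the −0.19 above). HEI can change between stools and belongs in the model.
- *Marital status and activity level are not collected.* The questionnaire items are not shown and the medical record is also reviewed. All that can be said is that no source is named.
- *Recorded medication is ignored.* The list ends with medical history, which is undefined. Medication history sits in a form that the protocol calls a medical history questionnaire, so it may be included. Equally, the content of the interval history is not given, so antibiotic use between stools may or may not be recorded.
- *The taxon ROC models are wrong because they are unadjusted.* Their stated purpose is classification, which does not need confounder control. The point reaches them only where their results are read as associations for Aim 1.
- *Antidiarrheal use should be adjusted for, or exposed stools dropped.* Use of these drugs follows from diarrhea. Either step would condition on a consequence of CID and preferentially remove the patients whom Aim 1 studies.

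Two further objections carry weight. The outcome of the adjusted regression is not spelled out; reading it as the time contrast follows from its heading and entry rule. Covariates for individual models are also often left to an SAP, which is not shown here. But this protocol does itemise an adjustment set, and it attaches that set to the time contrast only.

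**Conclusion.** The point holds in this form. The taxon time contrast is adjusted for mostly fixed traits with no stated patient term, although the design is own-control. The between-patient CID association models are written without covariates.

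The size is uncertain. The 6-23% false positives per marker, against 4-5% adjusted, rest on assumed confounder strengths, and the low end is negligible. They are rates for a single test at nominal 5%, not the error rate of the planned FDR procedure. No rate can be given for taxa wrongly attributed to FOLFOX because of other drugs: the share exposed, the drug effect and the within-patient variability are not in the protocol.

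The changes are cheap improvements on the stated method and are worth making before the data are analysed.

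**What to change.** 1. **Time-contrast models.** Include a patient term in DESeq2 and in the follow-up regression, and keep HEI as a time-varying covariate. Add an indicator for systemic antibiotic use between stools where the interval or medication history records it. Pre-operative intravenous antibiotics are given in all cases (Tissue Biofilm Quantification), so no indicator can separate them from the change since the pre-surgery stool. The post-surgery, pre-treatment stool is the cleaner baseline for the FOLFOX contrast. Do not adjust for antidiarrheals, or exclude stools exposed to them, in the main analysis.
2. **CID models.** Adjust each taxon and metabolite association for a short prespecified set, such as age, sex, stage, site and tobacco. For the classification analysis, report the AUC gained over a clinical model with the same set.
3. **Covariate list.** Name the source of marital status and activity level, or drop them. Define medical history and say whether it includes medication.

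The cost is protocol wording and some analysis work. The statistical price is about 5 degrees of freedom with roughly 56 CID events, if CID affects about half of 112 patients. If the rate is well above one half, the smaller non-CID group sets the limit and the set should stay short.
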